#### **Confidentiality Statement**

negative. The derivation of  $cC_t$  from  $C_t$  values BLOQ will follow rules specified in section 12.1.5.

To evaluate the applicability of this background-correction method, the number of subjects for whom  $\lambda_z$  can be robustly estimated from the PK samples collected at Days 4 to 5 (see section 7.1.2.3 "Criteria for Calculating the Apparent Terminal Elimination Half-Life") will be considered, as this will limit the number of evaluable subjects for the background-corrected PK analysis.

If  $\lambda_z$  cannot be reliably estimated (see Section 7.1.2.3 "Criteria for Calculating the Apparent Terminal Elimination Half-Life") for a relevant number of subjects (e.g. for at least 80% of the PK population) then an alternative approach described in the next section will be evaluated.

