4.2 Rationale for Study Design

The minimum age of 21 years old in the inclusion criteria was selected based on the legal age of smoking in Switzerland (Canton of Ticino) of 18 years; and to account for the 3 years of smoking history.

Variants with two different nicotine contents (1 mg/product and 2 mg/product) will be tested. These two nicotine contents are evaluated in this study to identify which one would yield plasma nicotine concentrations as close as possible to those achieved after smoking a single cigarette. All of the subjects will initially use the lowest nicotine content product (P3P 3). The subject will be randomized to continue the study using the three remaining products (P3P 1, P3P 2 and P3P 4) containing 2 mg nicotine/product only on the Investigator’s judgment who will be responsible to assess safety information following the use of P3P 3.

Two product use regimens: fixed puffing and *ad libitum* use will be applied to provide insight into nicotine absorption. The fixed puffing regimen with consistent use conditions across subjects will be applied in order to minimize variability and thereby provide a better understanding of the respective impact of nicotine content, particle size and presence or not of a flavoring system in the different P3P variants with regards to nicotine PK profile. The *ad libitum* use period will provide information on nicotine PK and product acceptance when subjects use the P3P according to their own puffing behavior which is closer to a real-world setting.

Sampling timepoints for determination of nicotine concentrations were selected to ensure reliable estimation of PK parameters. In particular, frequent sampling during the first 15 minutes from T_0 fix will be performed in order to reliably assess t_{max} which is expected to be around 7 minutes, similar to what was observed with P3L (7) and cigarettes (8), and compatible with absorption by the pulmonary route.

Confidentiality Statement

Data and information contained in this document are considered to constitute trade secrets and confidential commercial information, and the legal protections provided to such trade secrets and confidential information are hereby claimed under the provisions of applicable law. No part of this document may be publicly disclosed without the written consent of Philip Morris Products S.A.

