Plasma nicotine presents a biphasic profile, with a typical rapid initial disposition half-life ($t_{1/2a}$) of 1.35 hours, followed by a slower terminal elimination half-life ($t_{1/2z}$) of 17 hours (11). To ensure a full nicotine washout between each product use, a separation of 3 days would have been required ($\sim 5 \times$ elimination $t_{1/2z}$). Based on nicotine population PK modeling, it was estimated that subjects nicotine has entered in the terminal elimination phase with concentrations decreasing according to the terminal elimination rate constant (λ_z) after 8 to 10 hours post administration. As a consequence, a minimum of 10 hours have been established in this study design between the start of each use regimen to ensure appropriate washout of nicotine. Background-concentration correction will be applied to adjust for carry-over effects with adjustment of baseline values to the estimated $t_{1/2z}$ (or the terminal elimination rate constant λ_z) which will be derived from additional blood sampling on Day 5 for each subject.

The use of estrogen contraceptive is known to accelerate nicotine clearance by 20% to 30% compared to women who do not take oestrogen contraceptive (12). Therefore, for the purpose of this study, use of hormonal contraception containing estrogens is prohibited. This also applies to hormone replacement therapy.

The activity of CYP2A6 will be measured. CYP2A6 activity drives the metabolism of nicotine to cotinine and subsequent metabolites. Nicotine metabolism by CYP2A6 varies between individuals of the same ethnicity/race and across ethnicity/race due to genetic variations. These genetic differences could be associated with reduced/increased nicotine metabolism (8).

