12.5 Primary Objectives and Endpoints

12.5.1 Primary Endpoint Analysis Variables

PK endpoints are listed in section 3.1.

Nicotine PK parameters for fixed puffing regimen will be derived from plasma nicotine concentration versus time data using a non-compartmental analysis (NCA) technique using Phoenix WinNonlin, Version 7.0 or higher.

To minimize the carry-over effect in the nicotine plasma PK parameters due to limited washout periods (see Section 4.2), background-concentration correction will be applied to the concentration data for the fixed puffing regimen and *ad libitum* use. The baseline correction will be implemented by calculating the nicotine exposure parameters using adjusted concentration values as described below.

The nicotine terminal elimination rate constant λ_z (and $t_{1/2z}$) will be estimated from the Day 5 PK samples by using a linear regression on the log plasma nicotine concentration data. The regression analysis should contain data from at least 3 different time points in the terminal phase (including the last quantifiable concentration but excluding the concentration at t_{max}), consistent with the assessment of a straight line on the log- transformed scale. The nicotine plasma background-corrected PK parameters will be derived by performing the NCA on the corrected concentrations.

For the purposes of background-correction of the plasma concentrations post-baseline the following formula will be applied: $cC_t = C_t - C_0 \cdot e^{-\lambda_z t}$. Where, cC_t is the corrected concentration at each time point, C_t is the concentration at each time point, C_0 is the pre-use baseline concentration, λ_z is the Day 5 terminal elimination rate constant and t is the actual time.

The procedure of the baseline adjustment will be detailed in the SAP.

If plasma concentrations cannot be background-corrected in a sufficient number of subjects, alternative analysis methods will be used, as detailed in the SAP.

Confidentiality Statement

Data and information contained in this document are considered to constitute trade secrets and confidential commercial information, and the legal protections provided to such trade secrets and confidential information are hereby claimed under the provisions of applicable law. No part of this document may be publicly disclosed without the written consent of Philip Morris Products S.A.

In particular, the following PK parameters will be derived from nicotine levels adjusted for baseline:

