#### Goodness of Fit

- When assessing apparent terminal phases, the coefficient of determination,  $R^2$  adjusted value, will be used as a measure of the goodness of fit of the data points to the determined line. This parameter will be used as it is considered to be a better assessment of the goodness of fit, compared to  $R^2$ , as it adjusts for the number of points included in the line therefore allowing for a more direct comparison between elimination phases determined using different numbers of data points.
- Apparent terminal half-life will only be calculated if the  $R^2$  adjusted value of the regression line is greater than or equal to 0.700.

If the calculation of apparent terminal elimination half-life is performed according to the compartmental analysis (CA), then it will be based on PK nicotine concentration samples from days 1 to 5 and all the considerations regarding the period of estimation, the number of data points included into the calculation and the goodness of fit will be no more applicable.

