### **13.1.3.3 Population PK Analysis Methodology (Non-Linear Mixed Effects Modelling)**

In the event that the two previously described PK analysis methods fail in background-correcting the data, a population PK analysis approach will be used.

This method will involve pooling the data from the present study with that of previous Philip Morris clinical studies and fitting this new dataset with the previously described population PK model by Marchand et al. (*Marchand et al., 2017*) to ultimately obtain the post hoc individual estimates of the PK parameters and the corresponding background-corrected individual PK parameters ( $C_{max}$ ,  $AUC_{(0-4h)}$ ) for subjects in study P3P-PK-01-CH.

Once individual parameters are obtained, PK simulations will be generated for each individual and P3P variant so as to obtain the corresponding background-corrected exposure PK parameters (e.g.  $cC_{max}$ ,  $cAUC_{fix(0-4h)}$ , etc.).

Similar to the compartmental analysis method, an important caveat for its applicability is that it requires knowledge of the actual nicotine exposure after both fixed puffing as well as ad libitum regimens (i.e. a reasonably accurate data on the nicotine input into systemic circulation over time).

The data will be explored graphically to evaluate its a priori fitness for modeling via this method (e.g. missing data, completion of the PK profiles, outliers etc.). If a population PK analysis methodology is to be considered a stand alone Modeling Analysis Plan (MAP) will be written. Although the final decision on the method for nicotine adjustment should be taken before the database lock, the MAP may be finalized after db lock.

In case the population PK method is also deemed unsuccessful, only the uncorrected PK parameters will be reported and used for statistical analyses.

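### Background correction depends on each subject having a reliable λz of their own, with no fallback value, although the subtraction over 0–4 h is driven mainly by the measured baseline

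*SAP*

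**What the plan says.** Protocol 4.2 accepts that carry-over will be present: "To ensure a full nicotine washout between each product use, a separation of 3 days would have been required", while the design sets a minimum of 10 hours between starts of use. Protocol 12.5.1 and SAP 13.1.3.1 therefore correct each concentration: "For the purposes of background-correction of the plasma concentrations post-baseline the following formula will be applied", namely cCt = Ct − C0·exp(−λz·t), with C0 the pre-use sample of that session.

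Under the non-compartmental (NCA) method, λz comes from the subject's own Day 4–5 samples. SAP 7.1.2.3 sets conditions: at least three points, a span of at least 1.5 half-lives, and a fit criterion ("Apparent terminal half-life will only be calculated if the" adjusted R² reaches 0.700). SAP 13.1.3.1 judges the method by how many subjects meet them, "as this will limit the number of evaluable subjects for the background-corrected PK analysis". The trigger for moving on is given by example as failure "for at least 80% of the PK population".

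The second method, compartmental analysis (CA, SAP 13.1.3.2), applies the same formula with a model-predicted subject-specific λz and again counts subjects with a reliable value. Under CA, SAP 7.1.2.3 uses Days 1 to 5 and waives the NCA conditions. The third method is population PK. SAP 13.1.3.3 closes: "In case the population PK method is also deemed unsuccessful, only the uncorrected PK parameters will be reported and used for statistical analyses".

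Neither document gives a common or typical λz for a subject without one, or a sensitivity analysis on λz.

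**The concern.** C0 is sampled before every session. A subject who leaves after randomisation and before Day 5 is not replaced and has no Day 5 samples, so NCA cannot give that subject a λz. A subject whose regression fails the conditions is in the same position. Both lose every corrected parameter, although the main ingredient of the correction was measured each time.

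Corrected Cmax and AUC are the half of the primary objective that addresses carry-over. With three subjects per sequence, each lost subject removes within-subject information from the variant comparisons. The closing rule of 13.1.3.3 goes further: if λz cannot be settled by any method, no correction is made for anyone. The question is how much the correction really needs an individual λz.

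**Working it through.** **Inputs.** Half-life 17 h, the 10 h minimum separation and the 3-day washout statement (Protocol 4.2). Expected tmax for fixed puffing, "which is expected to be around 7 minutes" (Protocol 4.2). Correction formula (Protocol 12.5.1, SAP 13.1.3.1). Day 5 samples at 14, 16, 18, 20 and 24 h after T0 ad lib (Protocol 7.5.1). The ranges 10–30 h and 8.5–34 h (half to double 17 h) are assumptions.

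**1. The plan's washout figure.** 5 × 17 h = 85 h = 3.5 days, and 72 h is 4.2 half-lives, so the stated 3 days is about right. The 10 h minimum is 10/17 = 0.59 half-lives; 2^(−0.59) ≈ 0.67 of the terminal-phase level remains. Correction is needed.

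**2. How much λz matters to the subtraction.** With λ = ln 2 / T, the fraction of C0 removed at time t is exp(−λt). The area removed from AUC(0-4h) is A·C0, with A = (1 − exp(−4λ))/λ. The last column is the error in the correction term if 17 h is used for a subject whose true half-life is T, i.e. 3.691/A − 1.

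| T (h) | fraction at 7 min | A (h) | error from using 17 h |
|---|---|---|---|
| 8.5 | 0.990 | 3.413 | +8% |
| 10 | 0.992 | 3.493 | +5.7% |
| 17 | 0.995 | 3.691 | 0 |
| 30 | 0.997 | 3.821 | −3.4% |
| 34 | 0.998 | 3.841 | −4% |

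Making no correction omits 100% of the term.

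**3. What this does to cAUC.** With 17 h applied to everyone, reported minus true cAUC is (A − 3.691)·C0: −0.20·C0 if the truth is 10 h, +0.13·C0 if it is 30 h. As a percentage of cAUC this depends on C0 relative to the product's own contribution. The documents give no P3P concentrations, so these profiles are assumed: peak increment 3, 6 or 9.7 ng/mL at 7 min (9.7 is the P3L Cmax in Protocol 2.1.2), decline with half-lives 1.35 h and 17 h, terminal share 10–20%, C0 of 0.5 to 4 ng/mL, linear trapezoid at the protocol times. Applying a half-life of half or double the true 17 h gives:

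- cCmax moves by at most 0.6% in every case.
- cAUC moves by 0.4–6% for an increment of 9.7, and by up to 9% where C0 is at most two thirds of the increment. In those cases no correction inflates Cmax by 5–66% and AUC by 9–124%.
- In the extreme case (increment 3, C0 of 4), cAUC moves by −10.1% to +18.5%. No correction inflates that AUC by 227–248%.

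**4. The NCA gate is tied to half-life.** The longest reportable half-life is the sampling span divided by 1.5.

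- Day 5 samples only: (24 − 14)/1.5 = 6.7 h.
- From the 4 h sample on Day 4: (24 − 4)/1.5 = 13.3 h.
- An estimate of 17 h needs 1.5 × 17 = 25.5 h, longer than the whole interval from T0 ad lib to the last sample (24 h).

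So a subject whose estimate equals the protocol's typical value cannot pass.

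**5. How many could be left uncorrected under NCA.** Taking the PK population as the 18 randomised, 0.8 × 18 = 14.4. If the trigger means that NCA is kept when at least 15 succeed, up to 3 are uncorrected. Read literally (leave NCA when at least 15 fail), up to 14 are.

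**The case against.** The plan has a three-step hierarchy, announced in outline in the protocol. If half-lives are near 17 h, most subjects fail NCA and the plan moves to CA. CA uses Days 1 to 5 without the span, point-count and fit conditions, so even an early leaver may obtain a model-based λz. Population PK gives individual estimates by pooling with earlier studies, a more principled form of borrowing. Reporting uncorrected results alone is a third-level contingency. The SAP's revision history shows that the CA wording in 7.1.2.3 was clarified after draft interim PK results had been seen, so NCA-only loss may already be moot, although the SAP does not say which method was chosen.

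Subjects without λz also remain in the PK population and in every uncorrected summary and model; the primary objective covers both versions. The study is a descriptive pilot without hypotheses. And a percentage of the correction term is not a percentage of cAUC: step 3 shows that cAUC can move appreciably when C0 is high against a small increment. Day 1 is a plausible setting, since smoking is allowed until Admission, up to three test products follow, and the variant is the 1 mg one.

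All of this stands, and it limits the size of the problem. It does not supply the missing fallback. Section 13.1.3.2 still asks for a reliable λz after the criteria defining reliability have been waived, so who goes uncorrected under CA is open. Section 13.1.3.3 still ends with no correction. In every case examined, an approximate λz came closer to the corrected value than no correction did.

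**Conclusion.** The point holds as a cheap improvement. Making the correction depend on an individual λz discards, or in the last resort abandons, a usable adjustment. A common 17 h value misstates the correction term by about −3% to +6% for true half-lives of 10 to 30 h (−4% to +8% for 8.5 to 34 h), against 100% for none. For cCmax the choice of λz is nearly irrelevant. For cAUC the sensitivity is small at low to moderate C0 and larger when C0 is high.

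This rests on the SAP formula, the protocol's 17 h, the protocol's premise that decline is terminal by 8 to 10 h, and an assumed half-life range. The concentration examples are illustrations only.

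Three stronger readings are not supported:

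- A reader might infer that the R² rule screens out long half-lives at a rate that can be calculated. The documents give no residual variability, and the 1.5 half-life rule would bind first. If nearly everyone then fails, the plan moves to CA rather than analysing a selected remainder.
- A reader might infer that affected subjects leave the analysis, or that correction is likely to be lost for all. They leave only the corrected analysis, and total loss requires three failures.
- A reader might infer that corrected results as a whole are insensitive to λz. That holds for cCmax and for the correction term, but not for cAUC in general.

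**What to change.** In SAP 13.1.3.1 and 13.1.3.2, state that any PK-population subject without a reliable own λz is corrected with a common value and flagged in the listings: the 17 h half-life of Protocol 4.2, or the median model-based λz if CA is run. The common value should not be the median of NCA passers alone, because the span rule makes that lean short. At its 6.7 h limit (A = 3.28) it would under-correct a 17 h subject by about 11%; at 13.3 h (A = 3.61), by about 2%.

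Replace the last sentence of 13.1.3.3 so that, if all methods fail, parameters corrected with 17 h are still reported beside the uncorrected ones.

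In both cases repeat the corrected analysis with a shorter and a longer assumed half-life, for example 10 h and 30 h, or half and double 17 h.

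The cost is SAP wording and two re-runs. The drawback is a shared λz for some subjects, with an error that is a small share of the correction term; the re-runs show whether it matters for cAUC.

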### **13.1.3.2 Alternative PK Analysis Methodology (CA-based method)**

Based on a visual examination of the concentration/time profiles, different potential compartmental PK models will be assessed. As a starting point, a two-compartment linear disposition combined with zero-order absorption model will be considered as this has previously been found to adequately describe the absorption phase and the biphasic disposition of plasma nicotine following administration via other smoking devices (*Marchand et al., 2017*).

For the purpose of this analysis the following assumptions in terms of nicotine exposure ("dose") will be made:

1. The nicotine content in the P3P capsule (1 or 2 mg) multiplied by the before and after use 'weight differential' ( $\Delta W = W_{\text{before}} - W_{\text{after}}$ ) is directly proportional to the nicotine intake ( $[\text{P3P capsule nicotine content} \times \Delta W] \propto \text{nicotine exposure}$ ) and will be used as a surrogate 'dose' for the inhaled nicotine exposure (intake) for the purposes of modelling, for both fixed and ad libitum regimens.
2. For fixed regimens, duration of puffing and the Human Puffing Topography (HPT) parameters are the same in all study subjects.
3. The smoking start and stop time will be used as the nicotine intake duration. For any other occasions where the nicotine exposures or duration of smoking are unknown (e.g. Day -1) these will be estimated during the model fitting.

After successfully fitting the individual plasma nicotine data with a PK model, the same approach described in Section 13.1.3.1 will be adopted to derive corrected nicotine levels by means of subject-specific  $\lambda_z$  predicted by the model. General equations for determination of  $\lambda_z$  from the parameters estimated in a two-compartment model are presented below:

### **13.1.3.3 Population PK Analysis Methodology (Non-Linear Mixed Effects Modelling)**

In the event that the two previously described PK analysis methods fail in background-correcting the data, a population PK analysis approach will be used.

This method will involve pooling the data from the present study with that of previous Philip Morris clinical studies and fitting this new dataset with the previously described population PK model by Marchand et al. (*Marchand et al., 2017*) to ultimately obtain the post hoc individual estimates of the PK parameters and the corresponding background-corrected individual PK parameters ( $C_{max}$ ,  $AUC_{(0-4h)}$ ) for subjects in study P3P-PK-01-CH.

Once individual parameters are obtained, PK simulations will be generated for each individual and P3P variant so as to obtain the corresponding background-corrected exposure PK parameters (e.g.  $cC_{max}$ ,  $cAUC_{fix(0-4h)}$ , etc.).

Similar to the compartmental analysis method, an important caveat for its applicability is that it requires knowledge of the actual nicotine exposure after both fixed puffing as well as ad libitum regimens (i.e. a reasonably accurate data on the nicotine input into systemic circulation over time).

The data will be explored graphically to evaluate its a priori fitness for modeling via this method (e.g. missing data, completion of the PK profiles, outliers etc.). If a population PK analysis methodology is to be considered a stand alone Modeling Analysis Plan (MAP) will be written. Although the final decision on the method for nicotine adjustment should be taken before the database lock, the MAP may be finalized after db lock.

In case the population PK method is also deemed unsuccessful, only the uncorrected PK parameters will be reported and used for statistical analyses.

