### 3 INTRODUCTION

This SAP has been developed to supplement the statistical analyses described in the clinical study protocol final version 1.0 dated 24 July 2017.

This SAP describes the methodology and considerations of the planned analyses and a list of all the TFLs for this study. A detailed description of the planned TFLs will be provided in a separate TFL shells document. Any changes to the TFL shells numbering or to the title of the TFLs will not require an amendment to this SAP.

This SAP and any amendments will be finalized prior to the lock of the clinical database. Any changes to the analyses described in this document or additional analyses performed to supplement the planned analyses, will be described in the clinical study report (CSR).

The preparation of this SAP is based on the following documents:

- International Conference on Harmonisation (ICH) E9 guideline entitled, "Guidance for Industry: Statistical Principles for Clinical Trials" (**ICH Guideline E9, 1998**).
- ICH E3 guideline entitled, "Guidance for Industry: Structure and Content of Clinical Study Reports" (**ICH Guideline E3, 1995**).
- Case report forms (CRF) final version 1.0 dated 25 AUG 2017.
- Randomization Plan version 2.0 dated 16 OCT 2017.

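### If the population PK fallback is used, corrected exposure is simulated instead of observed, and what would distinguish the 2 mg variants may be settled only after database lock

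*SAP*

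**What the plan says.** SAP 13.1 sets out three methods of background correction, tried in order.

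- **NCA (13.1.3.1).** λz is estimated for each subject, and the measured concentrations are corrected by cCt = Ct − C0·exp(−λz·t).
- **Compartmental analysis (13.1.3.2).** A model is fitted to each subject only to obtain λz. After that, "the same approach described in Section 13.1.3.1 will be adopted to derive corrected nicotine levels".
- **Population PK (13.1.3.3).** "In the event that the two previously described PK analysis methods fail in background-correcting the data, a population PK analysis approach will be used". The study data are pooled with earlier sponsor studies and a published model is refitted "to ultimately obtain the post hoc individual estimates of the PK parameters". Then "PK simulations will be generated for each individual and P3P variant so as to obtain the corresponding background-corrected exposure PK parameters".

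On dose, 13.1.3.3 says only: "Similar to the compartmental analysis method, an important caveat for its applicability is that it requires knowledge of the actual nicotine exposure". The one dose definition in the SAP is in 13.1.3.2, where capsule nicotine content times weight loss "will be used as a surrogate 'dose' for the inhaled nicotine exposure (intake) for the purposes of modelling, for both fixed and ad libitum regimens". Section 13.1.3.3 does not mention a product-variant effect or between-occasion variability.

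On timing, the choice of correction method is due before database lock, but "the MAP may be finalized after db lock". SAP section 3 says of the SAP itself: "This SAP and any amendments will be finalized prior to the lock of the clinical database".

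The primary PK parameters exist in corrected and uncorrected form (SAP 5.1). SAP 7.1.2 derives the uncorrected ones from measured concentrations, and both forms go through the same mixed model and the same three contrasts (12.6.1).

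**The concern.** In the first two tiers a corrected endpoint is a summary of what was measured, after a small subtraction. In the third it is the output of a model. A difference between variants can then reach cCmax or cAUC only through a quantity the model carries for that variant. If the only such quantities are the dose entered and its duration, a real difference in absorption at equal weight loss has no route into the result.

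The contrasts exposed to this are P3P 2 vs P3P 4 (particle size) and P3P 2 vs P3P 1 (flavour). Since the MAP may be completed after lock, the choices that decide whether these contrasts can respond to absorption may be made with the full data in hand.

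**Working it through.** There is no power or sample-size figure in the plan to reproduce here. The check is algebra, a small simulation, and a look at how much the correction depends on λz.

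**1. Algebra.** In a linear model, simulated exposure = dose × unit-dose profile (individual parameters, intake duration). With one parameter set per subject for all variants and equal intake duration, the profile cancels in a within-subject ratio, leaving dose ratio = (content × weight loss) / (content × weight loss). P3P 1, 2 and 4 all contain 2 mg (Protocol Table 1), so content cancels too and the weight-loss ratio remains.

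**2. Simulation.**

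From the documents: half-lives of 1.35 h and 17 h (Protocol 4.2), the protocol sampling times, 18 subjects in the six sequences, two compartments with zero-order input (SAP 13.1.3.2), and a fixed-use intake of 12 × 30 s = 0.1 h.

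Assumed: V1 = 100; k21 = 0.08/h; between-subject SD (log) 0.3 on CL and V1, 0.09 on Q and V2; residual SD (log) 0.15; weight-loss SD (log) 0.10. Individual least squares stands in for the population fit, with one simulated trial per scenario.

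- *Scenario A (assumed):* per unit of surrogate dose, P3P 4 delivers 1.30 times and P3P 1 0.80 times the nicotine of P3P 2, with equal expected weight loss. The realised weight-loss ratio was 0.97 for both contrasts, so the true ratios are 0.97/0.80 = 1.21 and 0.97/1.30 = 0.75.
- *Scenario B (assumed):* equal nicotine delivery, but flavoured variants lose 1.25 times the weight. Here 1.25 is the upper end of a range. Powder mass is 2 mg/0.05 = 40 mg; if the 4:1 blend is by mass and flavour is added on top, it adds 10 mg, and 50/40 = 1.25. If total fill is equal, the figure is 1.00.

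| Scenario and contrast | True | Weight-loss ratio | One parameter set per subject | Variant bioavailability fitted |
|---|---|---|---|---|
| A, P3P 2/P3P 1 | 1.21 | 0.97 | 0.97 | 1.19 |
| A, P3P 2/P3P 4 | 0.75 | 0.97 | 0.97 | 0.74 |
| B, P3P 2/P3P 1 | 0.97 | 1.21 | 1.21 | 0.95 |
| B, P3P 2/P3P 4 | 1.04 | 1.04 | 1.04 | 1.04 |

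Results were the same for cCmax and cAUC. A shared parameter set returns the weight-loss ratio exactly: it hides real effects in A and creates a flavour effect in B. A variant term recovers the true ratios closely.

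**3. Is full simulation needed?** The fraction of C0 still to be subtracted at time t is 2^(−t/half-life).

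| Half-life | At 7 min (expected tmax, Protocol 4.2) | At 4 h |
|---|---|---|
| 10 h (assumed) | 0.992 | 0.76 |
| 17 h (Protocol) | 0.995 | 0.85 |
| 24 h (assumed) | 0.997 | 0.89 |

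Across that range the subtraction changes by at most 0.13 × C0 at 4 h and hardly at all near the peak. A model-supplied λz applied to observed data is therefore enough.

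**The case against.** The strongest reply is that much of the worry is drawn from silence. The weight-loss surrogate is introduced for the compartmental analysis, and 13.1.3.3 does not repeat it. That section asks for reasonably accurate data on input into the systemic circulation and names this as a caveat on the method's use. The published model, as refitted, might carry product or occasion terms; the documents do not say. This stands. A reader might infer that the corrected contrasts *will* be weight-loss ratios, but the text supports only that they *could* be.

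Three other stronger readings also fail.

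- *That all primary endpoints become simulated.* The uncorrected parameters stay on measured data with the same contrasts, so an absorption difference would still show there, diluted by background.
- *That a late MAP breaches SAP section 3.* That sentence covers the SAP and its amendments. The MAP is a stand-alone document, and the choice of method is due before lock. Protocol 12.5.1 and 12.7 also allow alternatives to NCA.
- *That shrinkage removes real variation.* Each subject gives 4 × (10 + 8) + 5 = 77 samples, and nothing in the documents shows material shrinkage.

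It is also fair that this is the third tier of a descriptive pilot study, and that if it fails only uncorrected parameters are used. The SAP v2.0 changes made after the draft interim results include compartmental-specific half-life rules, which may mean this branch was not needed, though no section says which tier was chosen. Finally, a lock date does not make the MAP blind: the trial is open-label, and the interim report shows unadjusted PK by variant before lock.

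What remains is that 13.1.3.3 alone abandons observed data for the corrected endpoints and leaves the deciding model terms unspecified, possibly until after lock.

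**Conclusion.** The point holds in conditional form. If NCA and compartmental analysis both fail, the corrected endpoints come from simulation, unlike in the other two tiers. The corrected particle-size and flavour contrasts then could reduce to weight-loss ratios under three conditions: the 13.1.3.2 surrogate is used as the dose, no variant- or occasion-level bioavailability term is fitted, and intake duration is equal. The SAP leaves the first two open.

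Under those conditions the loss is complete, not partial: in Scenario A, ratios of 1.21 and 0.75 both become 0.97, and in Scenario B a true 0.97 becomes 1.21. These sizes rest on the assumed inputs listed above. With a variant term the problem largely disappears. The uncorrected contrasts are unaffected in every case.

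**What to change.** In SAP 13.1.3.3, use the population model only to supply the individual λz (or the predicted residual background). Apply cCt = Ct − C0·exp(−λz·t) to the observed concentrations, then the same NCA and mixed model as in the other tiers. This matters more than the MAP's date, because it keeps the variant contrasts tied to measured concentrations whatever model terms are chosen.

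Require the MAP to be final before database lock and to state the dose input and any variant or occasion terms. Present the uncorrected contrasts alongside the corrected ones.

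The cost is a short change of SAP wording, plus MAP work moved before lock in a branch that may not be used.
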